3.8 Anti-drug Antibodies

The number and percentage of subjects who develop anti-MEDI8897 antibodies will be summarized at each visit by treatment group. For those with a positive assessment, the ADA titer results will also be summarized. The number and percentage of ADA positive samples with specificity to the YTE or neutralizing regions of MEDI8897 will also be summarized.

An additional table will summarize the number and percentage of subjects positive for ADA at baseline (ie, ADA prevalence) and positive at any post-baseline time point (ie, ADA incidence). For those with a positive post-baseline assessment, the percentage who were persistent positive and transient positive will also be presented.

1. Persistent positive is defined as positive at ≥ 2 post-baseline assessments (with ≥ 16 weeks between first and last positive) or positive at last post-baseline assessment
2. Transient positive is defined as negative at last one post-baseline assessment, and positive at only one post-baseline assessment or at ≥ 2 post-baseline assessments (with < 16 weeks between first and last positive)

To evaluate the impact of ADA on efficacy and safety, the primary and the secondary efficacy endpoints, as well as TEAE and SAE by SOC and PT based on MedDRA will be summarized by ADA status in three ways: 1) ADA post-baseline status (ie, at least one post-baseline ADA positive or not); 2) ADA persistent positive status (Yes or No); 3) ADA transient positive status (Yes or No).

The impact of ADA on PK will be included in the PK report as mentioned in Section 3.9.

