1.4 Summary of Clinical Experience

Two clinical studies of MEDI8897 have been conducted so far. The Phase 1a, first-time-in-human (FTIH) study (Study D5290C00001; ClinicalTrials.gov Identifier NCT02114268) in healthy adult volunteers was completed in June 2015, and the second study, a Phase 1b/2a study (D5290C00002; ClinicalTrials.gov Identifier NCT02290340), in healthy preterm infants of 32-35 wGA has completed enrollment and dosing; follow-up is ongoing.

The FTIH study, D5290C00001, was a Phase 1a, randomized, double-blind, placebo-controlled, dose-escalation study to evaluate the safety and tolerability, PK, and ADA for MEDI8897 when administered as a single fixed dose of 300, 1000, or 3000 mg IV, or 100 or 300 mg IM to healthy adult subjects. Subjects completed 1 year of follow-up in June 2015. A total of 136 subjects were randomly assigned to receive a single dose of MEDI8897 (6 subjects each at doses of 300 mg IV, 1,000 mg IV, 3,000 mg IV, and 100 mg IM; 78 subjects at 300 mg IM) or placebo (34 subjects). The mean $t_{1/2}$ of MEDI8897 ranged from 85 to 117 days across the IV and IM dose groups, and model-estimated systemic bioavailability after IM administration was 87%. The predicted 3- to 4-fold increase in the $t_{1/2}$ of MEDI8897 compared to a standard immunoglobulin G (IgG) antibody was confirmed. In healthy adults, the safety profile of MEDI8897 was favorable, with similar proportions of adverse events (AEs) reported in placebo (21/34; 61.8%) and MEDI8897 recipients (64/102; 62.7%). Two SAEs (gunshot wound and appendicitis) were reported in 2 MEDI8897 recipients. AEs judged to be related to study drug were reported in 29.4% (10/34) of placebo recipients and 17.6% (18/102) of MEDI8897 recipients. The most frequently reported AEs in the MEDI8897 cohorts were upper respiratory tract infection (URTI; 19/102; 18.6%), headache (9/102; 8.8%), urinary tract infection (UTI; 6/102; 5.9%); and dermatitis contact, musculoskeletal pain, nausea and vomiting (5/102, 4.9% each). All other AEs occurred in 4 or fewer subjects. There were no events designated as adverse events of special interest (AESI). One event of Type 2 diabetes was reported as a new onset chronic disease (NOCD) in the placebo group. There were no deaths. No safety signals in this healthy adult population were observed. Post-baseline ADA was detected in a similar proportion of placebo recipients (5/33, 15.2%) and MEDI8897 recipients (14/102, 13.7%), and the presence and titer of ADA

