2.2.2 Secondary Endpoints

1. Incidence of hospitalizations due to RT-PCR-confirmed RSV over the duration of the 5-month RSV season
2. Safety and tolerability of MEDI8897 as assessed by the occurrence of all treatment-emergent adverse events (TEAEs), treatment-emergent serious adverse events (TESAEs), AESIs, and NOCDs
3. Single-dose MEDI8897 serum concentrations

4. Incidence of ADA to MEDI8897 in serum

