3.2.3 Rationale for Endpoints

MEDI8897 is being developed to provide RSV immunoprophylaxis for all infants entering their first RSV season. The primary endpoint will examine the efficacy of MEDI8897 compared to placebo in preventing LRTI due to RSV. Respiratory syncytial virus results in a significant burden of disease consisting of hospitalization, visits to the ER, and visits to outpatient clinics. This primary endpoint is designed to allow the capture of this total burden of disease and the efficacy of MEDI8897 in reducing that burden.

A separate secondary endpoint of RSV hospitalization, which would indicate the most serious illnesses, will also be evaluated. Additionally, descriptive statistics of the serum concentrations of MEDI8897 at selected time points will be evaluated as a secondary endpoint and to confirm that serum concentrations are maintained above the target value of

6.8 µg/mL for 5 months. The serum concentration data will be used to characterize the PK of MEDI8897 in infants using a population PK approach. For infants who require hospitalization for LRTI, an additional serum sample for measurement of MEDI8897 concentration and ADA will be obtained around the time of hospitalization. Exposure-response analysis will be performed to relate MEDI8897 serum concentrations and efficacy endpoints (LRTI including RSV-associated hospitalization).

To determine the duration of MEDI8897 serum levels post dosing and to correlate with the development of ADA, serum concentrations will be measured at 360 days post dosing. ADA will be measured at selected time points throughout the study and at 360 days post dosing, when MEDI8897 levels are expected to be low and to not interfere with detection of ADA, if present.

Exploratory endpoints will examine magnitude of healthcare resource utilization and caregiver burden due to RSV illness in the current population. This will allow the determination of social and economic resources that are required for infants who have LRTI.

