4.8.5.2 Analysis of Anti-drug Antibodies

The incidence of ADA to MEDI8897 will be assessed and summarized by number and percentage of subjects that are ADA positive by treatment group. The ADA titer will be listed by subject at different time points. The impact of ADA on PK, and association with TEAEs and TESAEs will be assessed.

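### ADA incidence is defined as any post-baseline positive whatever the pre-dose result, so infants already positive at baseline who stay positive are counted as incident

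*SAP*

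**What the plan says.** The protocol lists "Incidence of ADA to MEDI8897 in serum" as a secondary endpoint (Section 2.2.2). Its analysis section (4.8.5.2) says only that ADA will be "summarized by number and percentage of subjects that are ADA positive by treatment group", and adds a by-subject listing of titers over time. A pre-dose ADA sample is scheduled at screening (Table 4.2.1-1).

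The working definitions are in SAP version 5, Section 3.8:

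- By visit: "The number and percentage of subjects who develop anti-MEDI8897 antibodies will be summarized at each visit by treatment group".
- Overall: one table counts infants "positive for ADA at baseline (ie, ADA prevalence) and positive at any post-baseline time point (ie, ADA incidence").
- Persistent positive: either two or more post-baseline positives at least 16 weeks apart, "or positive at last post-baseline assessment".
- Impact on outcome: the primary and secondary efficacy endpoints, TEAEs and SAEs are summarized by ADA status. The first grouping is "ADA post-baseline status (ie, at least one post-baseline ADA positive or not"); the other two are the persistent and transient classes.

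None of these rules uses the baseline result. No other section of the protocol or SAP adds a baseline exclusion or a titer-rise rule, and the definition is the same in all five SAP versions in the file.

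**The concern.** Incidence and prevalence are different quantities, and the SAP uses both words. The by-visit summary also speaks of infants who develop antibody. The rule as written cannot identify who developed it. An infant reactive before dosing and unchanged afterwards appears in both the prevalence row and the incidence row, and is persistent positive if the last sample is positive.

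Two outputs are affected. The first is the incidence figure for the secondary endpoint. The second is the set of ADA-status groups used to look for an effect of ADA on efficacy and safety, which bears on the safety part of the third secondary hypothesis. If pre-existing reactors make up much of the positive group, a real effect of newly formed antibody could be diluted.

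**Working it through.** The documents give no ADA rate, sample size or power for this endpoint, so there is no planned figure to reproduce. The check is to compare what the SAP rule would report with what a baseline-conditioned rule would report.

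**Inputs, all assumed because the documents do not give them:**

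- b = baseline prevalence: 2%, 5%, 10%
- s = share of baseline positives with at least one post-baseline positive: 0%, 50%, 100%
- e = emergent rate among baseline negatives on MEDI8897: 4%
- no baseline positive shows a titer rise

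**Formulas:**

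- SAP incidence in one arm = b·s + (1 − b)·e
- Treatment-emergent incidence over all evaluable infants = (1 − b)·e
- Pre-existing share of the ADA-positive group = b·s / [b·s + (1 − b)·e]
- Active minus placebo under the SAP rule, with the same b and s in both arms and no emergent positivity on placebo = [b·s + (1 − b)·e] − b·s = (1 − b)·e

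Example, b = 5% and s = 100%: 0.05 + 0.95 × 0.04 = 0.088, or 8.8%. The pre-existing share is 0.05 / 0.088 = 57%. The difference from placebo is 8.8% − 5.0% = 3.8%.

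| b | SAP incidence, s = 0% | s = 50% | s = 100% | Pre-existing share, s = 100% | Active minus placebo, any s |
|---|---|---|---|---|---|
| 2% | 3.9% | 4.9% | 5.9% | 34% | 3.9% |
| 5% | 3.8% | 6.3% | 8.8% | 57% | 3.8% |
| 10% | 3.6% | 8.6% | 13.6% | 74% | 3.6% |

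Read down one arm with full persistence, the reported figure is 1.5, 2.2 and 3.4 times the assumed 4%. With no persistence there is no inflation. The between-arm difference stays within 0.4 percentage points of 4% in every row and errs slightly low.

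**The case against.** **The reader has context.** Baseline prevalence is in the same table, results are given by arm with a randomized placebo group, and the protocol promises a by-subject titer listing. This largely stands. The placebo contrast removes the pre-existing component from the incidence comparison, and the listing would let a determined reader rebuild the overlap. It does not change the tabulated endpoint or the make-up of the ADA-positive groups, and no cross-classification of baseline by post-baseline status is planned.

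**The endpoint is descriptive.** This stands. No test or decision rule depends on it. The SAP never calls the positives drug-induced; that sense comes only from the words incidence and develop.

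Some stronger readings go beyond the documents:

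- *Background positivity is known to be large.* In the adult study, "Post-baseline ADA was detected in a similar proportion of placebo recipients (5/33, 15.2%) and MEDI8897 recipients (14/102, 13.7"%), and the infant study reports placebo positives at its 30-day interim analysis. The adult figure is explicitly post-baseline and the infant figure is not a baseline rate. Neither shows pre-existing reactivity, and if those placebo recipients were negative before dosing, a baseline rule would still count them as emergent.
- *Circulating drug hides ADA at Days 91 and 151.* Protocol Section 3.2.3 describes 360 days as the time "when MEDI8897 levels are expected to be low and to not interfere with detection of ADA". It does not say that earlier samples are unusable, and no assay drug-tolerance figure is given.
- *Day 361 is not shown separately.* The by-visit summary already covers it.
- *Untested infants are counted as negative.* Section 3.8 states no denominator or missing-sample rule. That is silence, not a rule.
- *The effect of ADA on PK is distorted.* That analysis is deferred to a separate PK report, which is not available here.

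**Conclusion.** The definition does count baseline positives who remain positive as incident, and nothing elsewhere in the plan corrects it. It affects a listed secondary endpoint, the persistent and transient classes, and the efficacy, TEAE and SAE summaries by ADA status.

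The size cannot be established. A single-arm incidence of 5.9% to 13.6% requires the assumed 4% emergent rate, 2% to 10% baseline prevalence and full persistence; with prevalence near zero or no persistence the effect disappears. A reader might infer from those figures that the treatment comparison is inflated by the same factor. It is not: under the same assumptions the active-minus-placebo difference is slightly understated.

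The more durable problem is the composition of the ADA-positive group, because the summaries of outcome by ADA status do not separate pre-existing from new positivity within an arm. Alpha, power and the primary efficacy result are untouched.

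**What to change.** In SAP Section 3.8:

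1. Define ADA incidence as treatment-emergent: negative at baseline and positive post-baseline, or positive at baseline with a titer rise of a pre-specified size, which the sponsor should set from its own assay.
2. State the denominator: infants with a baseline and at least one post-baseline ADA result.
3. Use this status for the persistent and transient classes and for the efficacy, TEAE and SAE summaries.
4. Add a cross-tabulation of baseline by post-baseline ADA status, by treatment group.
5. Keep any post-baseline positive as a supporting row.

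The cost is SAP wording and programming. Baseline samples, post-baseline samples and titers are already planned. The drawback is a smaller ADA-positive group, and so less precise summaries within it. The reduction depends on how many baseline positives there are and how many persist.

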4.3.5 Anti-drug Antibody Response Evaluation and Methods

Blood samples will be collected to evaluate ADA responses to MEDI8897 in serum (see [Table 4.2.1-1](#) and [Table 4.2.2-1](#) for the schedule of tests) at screening and on Day 91, Day 151 and Day 361 and as needed (ADA samples will be collected for subjects hospitalized with LRTI within 2 days and up to 14 days following hospitalization; see [Table 4.2.1-1](#) and [Table 4.2.2-1](#) for schedule of tests). Evaluations will be performed by MedImmune, using a validated immunoassay.

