5 ASSESSMENT OF SAFETY

5.1 Definition of Adverse Events

The ICH Guideline for Good Clinical Practice E6 (R1) defines an AE as:

Any untoward medical occurrence in a patient or clinical investigation subject administered a pharmaceutical product and which does not necessarily have a causal relationship with this treatment. An AE can therefore be any unfavorable and unintended sign (including an abnormal laboratory finding), symptom, or disease temporally associated with the use of a medicinal product, whether or not considered related to the medicinal product.

An AE includes but is not limited to any clinically significant worsening of a subject's pre-existing condition. An abnormal laboratory finding (including electrocardiogram [ECG] finding) that requires medical intervention by the investigator, or a finding judged by the investigator as medically significant should be reported as an AE. If clinical sequelae are associated with a laboratory abnormality, the diagnosis or medical condition should be reported (eg, renal failure, hematuria) not the laboratory abnormality (eg, elevated creatinine, urine red blood cells [RBC] increased). Abnormal laboratory values that are not, in the investigator's opinion, medically significant and do not require intervention should not be reported as AEs.

Adverse events may be treatment emergent (ie, occurring after initial receipt of investigational product) or nontreatment emergent. A nontreatment-emergent AE is any new sign or symptom, disease, or other untoward medical event that begins after written informed consent has been obtained but before the subject has received investigational product.

Elective treatment or surgery or preplanned treatment or surgery (that was scheduled prior to the subject being enrolled into the study) for a documented pre-existing condition that did not worsen from baseline is not considered an AE (serious or nonserious). An untoward medical event occurring during the prescheduled elective procedure or routinely scheduled treatment should be recorded as an AE or SAE.

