5.5.1 Time Period for Collection of Adverse Events

Adverse events and SAEs will be collected from the time of signature of informed consent through the follow-up period (Day 361 visit).

All AESIs and NOCDs will be collected from the time of dosing through the follow-up period (Day 361 visit).

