1 INTRODUCTION

This document describes the statistical analysis plan (SAP) for protocol D5290C00003, a pivotal Phase 2b study to determine if MEDI8897 is efficacious in reducing medically attended respiratory syncytial virus (RSV)-confirmed lower respiratory tract infection (LRTI) in healthy preterm infants entering their first RSV season. The primary efficacy hypothesis of this study is that, compared with placebo, a single 50-mg intramuscular (IM) dose of MEDI8897 will be efficacious in reducing medically attended LRTI caused by reverse transcriptase-polymerase chain reaction (RT-PCR)-confirmed RSV in healthy preterm infants born between 29 weeks 0 days and 34 weeks 6 days gestational age (GA) and entering their first RSV season, and the safety profile will be acceptable. The secondary hypotheses are that (1) there will be a reduction in the incidence of hospitalizations attributable to RSV, (2) the predicted extended terminal half-life ($t_{1/2}$) will be adequate for the duration of the RSV season, and (3) anti-drug antibodies (ADA) to MEDI8897 will not significantly impact the serum concentrations or safety of MEDI8897 over the 5-month RSV season. These hypotheses will be assessed by the incidence of RSV LRTI, RSV hospitalization, ADA, pharmacokinetic (PK) parameters, and descriptive statistics from safety data. This document details the statistical summaries relating to each study objective and describes the general conventions and definitions that will be used.

In addition, a set of table templates and specifications is planned to be created in a statistical programming plan to complement this document.

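### SAP v5 3.8 splits TEAEs and SAEs by ever-positive ADA status without regard to whether the event came before or after ADA was found

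*SAP*

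**What the plan says.** Section 3.8 of SAP v5 sets out to evaluate the impact of ADA on safety through tables in which the endpoints "as well as TEAE and SAE by SOC and PT based on MedDRA will be summarized by ADA status in three ways". The first split is "at least one post-baseline ADA positive or not"; the other two are persistent positive (yes or no) and transient positive (yes or no). A single positive at the last assessment is enough to be called persistent. No split refers to when an event began.

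The surrounding text fixes the time frame:

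- Protocol 5.1: "Adverse events may be treatment emergent (ie, occurring after initial receipt of investigational product".
- Protocol 5.5.1: "Adverse events and SAEs will be collected from the time of signature of informed consent through the follow-up period (Day 361 visit".
- Protocol 4.3.5: ADA is sampled "at screening and on Day 91, Day 151 and Day 361 and as needed". The as-needed sample is taken only when an infant is hospitalized with LRTI.
- Protocol 3.2.3: the Day 360 sample is taken "when MEDI8897 levels are expected to be low and to not interfere with detection of ADA, if present".
- SAP v5 3.7.6: the planned split of adverse events by time is relative to dosing, not to ADA.
- SAP v5 3.7: safety analyses use the As-treated population, which does not require an ADA sample.

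The hypothesis these tables serve, in the SAP Introduction, is that ADA "will not significantly impact the serum concentrations or safety of MEDI8897 over the 5-month RSV season".

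**The concern.** ADA status is learned during follow-up but is applied back to Day 1. An infant first found positive at Day 361 is labelled ADA-positive, and also persistent positive, for every event since dosing. If ADA raises the rate of some event, only the time after ADA appears carries the raised rate; the earlier time carries the background rate and averages the difference down.

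The 3.8 tables are the only ADA-by-event output the SAP plans for the safety part of the third secondary hypothesis. A reader who sees similar percentages in the two columns could not tell absence of effect from an effect averaged over time in which it could not act.

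Two lesser faults affect the comparator. The SAP does not say where an infant with no post-baseline result belongs. In addition, No in the persistent split includes transient positives, and No in the transient split includes persistent positives.

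**Working it through.** Section 3.8 gives no figure for these tables, so there is nothing to reproduce. The steps below use the visit schedule and stated assumptions.

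**1. Time elapsed before ADA can be found.** For a first positive at Day d, the share of the 360-day window already past is (d − 1)/360: 90/360 = 25% at Day 91, 150/360 = 42% at Day 151, and 360/360 = 100% at Day 361. Against the 5-month season named in the hypothesis, 90/150 = 60% has passed by Day 91.

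**2. Effect on a rate ratio.** Assume a constant background rate and a true ratio R that starts partway through. If s is the share of the window after it starts, the observed ratio is (1 − s) + R·s. With R = 2 this is 1 + s. Two starting points are used: midway between samples (Days 46, 121, 256), and the first positive sample itself.

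| First positive | s, midway | Observed | s, first detection | Observed |
|---|---|---|---|---|
| Day 91 | 315/360 = 0.875 | 1.88 | 270/360 = 0.75 | 1.75 |
| Day 151 | 240/360 = 0.667 | 1.67 | 210/360 = 0.583 | 1.58 |
| Day 361 | 105/360 = 0.292 | 1.29 | 0 | 1.00 |

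**3. Where that formula applies.** SAP v5 3.7.1 counts each adverse event once per infant, so the tables show proportions. With background 360-day incidence p and H = −ln(1 − p), the ratio of proportions is [1 − exp(−H(1 + s))]/p for R = 2. Using the first-detection values of s for Days 91, 151 and 361:

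- p = 2%: 1.74, 1.57, 1.00, against 1.98 if the effect ran for the whole window.
- p = 20%: 1.62, 1.49, 1.00, against 1.80.
- p = 70%: 1.25, 1.22, 1.00, against 1.30.

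Step 2 therefore describes event rates or rare preferred terms. For common events the ratio is compressed with or without the timing fault.

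**4. Infants with no post-baseline result.** Suppose they were counted as not positive. Let u be their share (assumed 2% to 10%), a the ADA prevalence (assumed 5% to 15%), and f the day they left (15 to 90). Relative to a fully followed never-positive infant, the comparator's event risk is [(1 − u)(1 − a) + u·f/360] / [(1 − u)(1 − a) + u]. With u = 5%, a = 5%, f = 45 this is 0.90875/0.9525 = 0.954, so a true ratio of 1 shows as 1.05 and a true 2 as 2.10. Over the whole range, 1 shows as 1.02 to 1.13 and 2 as 2.03 to 2.25, so the contrast is inflated. If the untested infants were instead fully followed, with undetected ADA at prevalence a, a true 2 shows as 1.97 to 2.00.

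**5. Mixed comparator in the persistent split.** Assume half of the positives are transient and all positives carry a whole-window ratio of 2. At 5% prevalence the comparator is (0.95 + 2 × 0.025)/0.975 = 1.026, so 2 shows as 1.95. At 15% it is (0.85 + 2 × 0.075)/0.925 = 1.081, so 2 shows as 1.85.

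**The case against.** The strongest objection is that the first positive sample is not the onset of ADA. Sampling is sparse, and Protocol 3.2.3 implies that circulating drug can interfere with detection until about Day 361, so an event on Day 10 in an infant first positive at Day 361 is not shown to precede ADA. Protocol 5.3.2 says serum sickness typically appears 1 to 2 weeks after first exposure, before any routine sample. An ever-positive split keeps such events in the ADA group; a table restricted to events after the first positive would lose them, and would leave almost no time for infants first positive at Day 361. This stands. It rules out replacing the ever-positive tables, but not adding to them.

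A reader might also infer that untested infants are counted as not positive and that this hides harm. The SAP does not state such a rule. In Protocol 1.4 the infant ADA rates of 12.5% and 4.4% match 2/16 and 3/68 rather than the printed 2/18 (11.1%) and 3/71 (4.2%), which suggests tested denominators in that study. Even on the literal reading, early leavers lower the comparator and inflate the contrast. The extra sample at LRTI hospitalization also ties testing to a serious event and can push the same way.

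Finally, the tables are descriptive, with no test or decision rule, and Protocol 4.8.5.2 has ADA titer listed by infant and time point, so individual cases can be examined. That limits the consequence, but leaves the summary tables without time order.

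**Conclusion.** The point holds for time order. Section 3.8 applies a status that may be learned as late as Day 361 to events from Day 1. Given a stable background rate and an event rate that rises once ADA appears, the contrast moves toward the null: a true rate ratio of 2 shows as 1.29 to 1.88 under midway onset, or 1.00 to 1.75 if the effect starts at first detection. These are illustrations; the documents do not give this trial's ADA timing, prevalence or event rates.

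It does not follow that every ADA harm is diluted or that a conclusion of no impact is bound to be drawn. Most of the illustrated ratios stay above 1, the comparator faults can push either way, and nothing formal is decided on these tables. For untested infants, the supportable finding is that the rule is missing. The matter concerns how the third secondary hypothesis can be interpreted, and a cheap addition to the SAP would improve it.

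**What to change.** Keep the three ever-positive tables in 3.8 and add the following:

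- For ADA-positive infants, tabulate TEAEs and SAEs by onset before the last negative sample, between the last negative and first positive samples, and on or after the first positive sample. Give exposure time in each band, and show ADA-negative infants over the same visit intervals as reference.
- Show infants with no valid post-baseline ADA result as a separate row.
- Use never-positive infants as the comparator in all three splits.
- State the limits beside the tables. Counts will be small: if the earlier infant study's 4.4% carried over, 1,000 × 0.044 = about 44 positives among dosed infants. Infants first positive at Day 361 have almost no time in the last band. A negative sample before Day 361 may reflect drug interference, so early events must not be dropped.

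The cost is SAP wording and table programming. Event onset dates and ADA sample dates are already collected, and trial conduct does not change.
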